2.1 Study Design

Overview

1) Pre-Exposure Prophylaxis Provision in the Emergency Department (PrEPPEDE) RCT

We aim to assess the feasibility of initiating ED patients onto HIV PrEP. Specifically, among 80 PrEP eligible patients, this randomized controlled trial will compare the strategies of: a) ED screening with immediate PrEP (iPrEP) initiation, discharge with 14-day PrEP starter packs and facilitated linkage to outpatient care; vs. b) ED screening with facilitated linkage to an outpatient care for PrEP initiation. The primary outcome of interest is PrEP usage at 90 days with multiple exploratory secondary outcomes including PrEP adherence at 30, 60 and 90 days, retention in care, STI diagnosis, risk factor modification and program satisfaction. The intent of the proposed study is to provide data on recruitment and attrition rates, as well as means and standard deviations for key measures that will be needed to plan a definitive multicenter trial of ED-initiated PrEP.

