7.0 Randomized Controlled Trial

7.1 Primary Aim:

Among 80 PrEP eligible patients compare in a pilot 1:1 RCT design, the strategies of a) facilitated linkage for PrEP initiation within 14-days of ED visit and b) immediate PrEP (iPrEP) initiation in the ED, a 14-day PrEP starter pack at discharge and facilitated linkage.

The primary outcome is PrEP usage at 90 days post PrEP initiation visit. Secondary outcomes include retention in care, STI diagnosis, risk behavior and PrEP adherence at 30, 60, and 90 days.

7.2 Secondary/Exploratory Aims:

- (1) Retention in care at 30 and 60 and 90 days post PrEP initiation
- (2) PrEP usage at 30 and 60 days post PrEP initiation
- (3) PrEP adherence at 30, 60, and 90 days post PrEP initiation
- (4) Risk behavior at 30, 60, and 90 days post PrEP initiation
- (5) STI diagnoses at 30, 60 and 90 day follow-up visits
- (6) HIV infection
- (7) Program satisfaction

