11.1.2 Analysis of Primary and Secondary Outcomes

Analysis will be on an intention-to-treat basis. In statistical analyses, participants will be included to the date of their last active follow-up visit. Comparisons between control and experimental (iPrEP) arms. To assess the success of randomization, a summary of the baseline variables by treatment group will be tabulated and univariate comparisons performed. The primary outcome, retention in care and PrEP usage, will be compared with proportions and Fisher's exact derived confidence intervals. Secondary outcomes: Secondary analysis will focus on determining how retention in care, risk behavior, adherence or STI diagnosis differ between the groups at any of the follow-up time points. PrEP adherence based on pill counts will be calculated by dividing the number of pills taken by the number of pills prescribed. Adherence will be calculated by study month for each participant. Group adherence comparisons will be compared using Wilcoxon rank sum test. Retention in care, STI diagnosis and risk behavior at each time point will be analyzed for each study visit. Retention in care and STI diagnosis will be treated as dichotomous variables for analysis. Measures of risk behavior will include consistency of condom use and number of sexual partners since prior study visit. Condom use will be treated as an ordinal variable and number of sexual partners as a continuous variable for analysis.

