11.1.3 Sample Size

pilot RCT will be insufficiently powered to provide definitive efficacy data on retention and adherence for two study arms at 90 days. Yet, the pilot data is needed to determine recruitment and attrition rates, as well as means and standard deviations for key measures that will be needed to plan a definitive trial of ED-initiated

PrEP. For illustrative purposes we have included the following table of powers based on different retention in care rates in the control and experimental groups with the assumption that those retained in care will be using PrEP. This analysis assumes initial groups sizes of 40 and 40. The test statistic used is the two-sided Z test with pooled variance. The significance level of the test was targeted at 0.0500.

Power	Control Group	Experimental (iPrEP) Group	Difference in Proportions
	Retained in Care/PrEP	Retained in Care/PrEP	
0.0812	50%	55%	5%
0.1571	50%	60%	10%
0.2859	50%	65%	15%
0.4581	50%	70%	20%
0.6474	50%	75%	20%
0.8166	50%	80%	30%
0.9327	50%	85%	35%

The 50% follow-up rate for the control arm is based on and manuscript by Bogoch et als. entitled “Attrition Between the Emergency Department and Clinic Among Individuals Presenting for HIV Non-occupational Post exposure Prophylaxis published in *Clinical Infectious Diseases* in 2014.⁷⁴ The authors found that only 54% of patients seen in the ED for non-occupational post-exposure prophylaxis attended their first follow-up post-exposure clinic visit. This study did use appointment reminders but not the degree of facilitated linkage that will be used for the described ED PrEP program. In Project BRIEF, the HIV testing program described in the preliminary studies, the follow-up rate for newly infected HIV patients was 85%. Given that this will be the first effort at PrEP screening, initiation and linkage in the Emergency Department we do not expect to achieve the same degree of retention in care as we did for follow-up in Project BRIEF.

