12.2. Study Procedures, Materials, and Potential Risks

Aim 1

Study Procedures: Patients found to be eligible for PrEP will be randomized to immediate PrEP (iPrEP) initiation using a 14-day starter pack or PrEP initiation in the outpatient clinic. Both groups will have facilitated linkage to care. Follow-up study visits will occur at 30, 60 and 90days post PrEP initiation. The 30, 60 and 90 day assessments will over the phone.

Effective Date: 4/20/2021

End Date: 3/18/2022

Risks: Aim 1 involves randomization to one of two different PrEP initiation programs. PrEP initiation carries risks that would be considered more than minimal. Patients in both groups will be prescribed tenofovir disoproxil fumarate (FTC/TDF) which will be used for women and transgender men or

emtricitabine/tenofovir alafenamide (FTC/TAF) which will be used for men and transgender women. Both of these medications are FDA approved and is being used for its intended purpose in the population for whom it is indicated. Known physical risks of emtricitabine/tenofovir disoproxil fumarate and emtricitabine/tenofovir alafenamide are impaired renal function, intolerable side effects including nausea, vomiting or diarrhea as well as hypersensitivity reaction and osteopenia with long term use. Patients will also be subject to the same psychological and privacy and confidentiality risks.

Sources of Data: Aim 1 data sources will come from the following

- 1) Socio-demographic questionnaires collected during screening and enrollment
- 2) Behavioral risk factor questionnaires collected at enrollment and 30, 60, and 90day follow-up
- 3) PrEP attitude and knowledge measures
- 4) Satisfaction questionnaires collected during enrollment and 30 , 60, and 90-day follow-up
- 5) Laboratory reports obtained from the patient's electronic medical record at enrollment and 30 and 90-day follow-up
- 6) Locator forms collected to obtain correct contact information collected at enrollment and 30 and 60 day follow up
- 7) VSQ-9 study visit questionnaires collected at 30 and 90-day follow-up
- 8) Adherence questionnaires collected at 30, 60, and 90-day follow-up
- 9) Facility follow-up questionnaire

Data for Aim 1 will be collected using a touch screen tablet and paper and pencil surveys administered by the RA. All data will be linked to the individual study participant but will be de-identified for analysis.

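### The risk-behavior comparisons in section 11.1.2 use no enrollment value as a covariate and so give up precision; the size of the loss depends on a correlation the plan does not state

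*Combined protocol and SAP*

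**What the plan says.** Section 11.1.2 analyzes risk behavior visit by visit, using consistency of condom use and the number of partners since the preceding visit. The only further detail is the type of variable: "Condom use will be treated as an ordinal variable and number of sexual partners as a continuous variable for analysis". No test or model is named for these measures; the Wilcoxon test is named for adherence only. No covariate, change score or repeated-measures model appears anywhere in section 11. Baseline data have one planned use: "To assess the success of randomization, a summary of the baseline variables by treatment group will be tabulated and univariate comparisons performed".

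Enrollment data on risk behavior do exist. Section 9.3 lists the CSBQ among the measures for enrolled participants, and section 9.5 lists it again for follow-up, together with Section 4 of the ICAP screening form. Section 12.2 agrees: "Behavioral risk factor questionnaires collected at enrollment and 30, 60, and 90day follow-up". Section 2.1 describes the exploratory outcomes as including "risk factor modification and program satisfaction".

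**The concern.** People differ widely in sexual behavior. If part of that difference persists from enrollment to follow-up, it enters the between-arm comparison as noise that an enrollment covariate would remove. The data are already being collected, so leaving them out gives away precision that would cost almost nothing to keep. The trial is small, and its stated purpose includes supplying means and standard deviations for planning a definitive trial. A baseline-adjusted model would also yield the residual standard deviation and the baseline correlation, both useful for that planning. Finally, with no method named, the test and any covariates could be chosen after the data are seen.

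**Working it through.** **The plan's own figure.** The documents give no power, standard deviation or effect size for risk behavior. Their only power figures are in section 11.1.3, for retention in care/PrEP use, with 40 per arm and a 5% level. The method is given there: "The test statistic used is the two-sided Z test with pooled variance". Exact binomial enumeration of that test, with control at 50% and iPrEP at 55% to 85%, gives 0.0812, 0.1571, 0.2859, 0.4581, 0.6474, 0.8166 and 0.9327. All seven match the printed table to four decimals. (The 75% row prints a difference of 20%; 75% − 50% = 25%, and the printed power belongs to 25%.) This confirms the design inputs but says nothing about risk behavior.

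**Inputs for the check.**
- n = 40 per arm (section 11.1.3), allocated 1:1 (section 7.1: "compare in a pilot 1:1 RCT design").
- Follow-up of about 85% (section 17.2), so 0.85 × 40 = 34 per arm.
- Two-sided 5% level, borrowed from section 11.1.3.
- Correlation ρ between the enrollment and follow-up values: **an assumption**, taken over 0.2 to 0.7.

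**Formulas.** With a linear baseline covariate, the variance of the treatment contrast is multiplied by 1 − ρ² and its standard error by √(1 − ρ²). The equivalent unadjusted sample size is n/(1 − ρ²). The effect detectable with 80% power, in SD units, is (1.960 + 0.842) × √(2/n) × √(1 − ρ²). For rank, count or ordinal models these are approximations.

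**Results at 40 per arm.** Unadjusted detectable effect: 2.802 × √(2/40) = 2.802 × 0.2236 = 0.626 SD.

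| Assumed ρ | 1 − ρ² | SE ratio | SE reduction | Equivalent n per arm | Detectable effect (SD) |
|---|---|---|---|---|---|
| 0.2 | 0.96 | 0.980 | 2% | 41.7 | 0.614 |
| 0.3 | 0.91 | 0.954 | 5% | 44.0 | 0.598 |
| 0.5 | 0.75 | 0.866 | 13% | 53.3 | 0.543 |
| 0.7 | 0.51 | 0.714 | 29% | 78.4 | 0.447 |

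At 34 per arm the detectable effect is 0.679 SD unadjusted, 0.588 SD at ρ = 0.5 and 0.485 SD at ρ = 0.7.

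**Price of the covariate.** Estimating one extra coefficient inflates the variance by about 1 + 1/(2n − 4) = 1 + 1/76 = 1.013. At ρ = 0 the loss is therefore 1.3% of variance. At ρ = 0.2 the net factor is 0.96 × 1.013 = 0.973, still a gain.

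**Do the enrollment items match the outcome?** Not exactly.
- *Partners.* The analyzed count runs from the previous study visit, and no such visit precedes enrollment. The CSBQ partner item covers 12 months (Appendix 4) and the ICAP Section 4 item covers 6 months (Appendix 5).
- *Condom use.* CSBQ items are yes/no about the last occasion. ICAP asks one question about consistent use over 6 months. Neither shows an ordered consistency scale.
- *CSBQ at follow-up.* Sections 9.5 and 12.2 support repetition. Section 10.4.14 mentions enrollment only, and the list of follow-up assessments in section 10.5 omits the CSBQ.

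A covariate does not need the same recall window as the outcome; it only has to predict it. A change score does need the same window.

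**The case against.** The strongest reply is that this is a pilot that calls itself underpowered, that risk behavior is exploratory, and that unadjusted means and standard deviations serve the planning aim. That stands, and it sets the severity. It does not remove the point, because adjustment uses data in hand and costs about 1% of variance at worst.

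The reply also stands on size. Different recall windows, and enrolling only people who screen at substantial risk, could both hold the correlation down. At 0.2 to 0.3 the gain is slight.

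A reader might infer more than the documents support:

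- *That chance imbalance makes the comparison biased.* At 40 per arm the standard error of a baseline difference is √(2/40) = 0.224 SD, and a gap above 0.25 SD occurs in about 26% of trials. But that variation is already in the unadjusted standard error and type I error. It is added variance and a shift conditional on the particular allocation, not bias over randomizations.
- *That a large power gain is assured.* Simulated overdispersed counts (34 per arm, partner rate assumed halved) gave rank ANCOVA 50% power against 34% (Welch) and 32% (Wilcoxon) at a rank correlation near 0.65. A separate run with assumed mean 2 and shape 0.7, at a rank correlation near 0.33, gave 39% against 43% and 37%. The gain comes from assumptions that the plan neither makes nor supports.
- *That change from baseline is the declared estimand.* Only section 2.1 speaks of modification. Sections 2.0, 4.0, 7, 11.1.2 and 21.0 refer to risk behavior, and 11.1.2 asks how the groups differ at follow-up. A between-arm comparison answers that.
- *That the baseline comparisons are improper significance tests.* Section 11.1.2 does not mention p-values, so a descriptive comparison would comply. This is a side matter.

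**Conclusion.** The point holds as a matter of efficiency. Section 11.1.2 plans no baseline adjustment for risk behavior although enrollment risk data are collected. The loss ranges from negligible (standard error 2% larger than it need be relative to the unadjusted value, at ρ = 0.2) to substantial (29% at ρ = 0.7). The documents do not allow the true value to be placed within that range. The figures assume a roughly linear relation and 40 per arm with complete data. The omission is silence rather than a stated choice, since no method is named for these measures. Severity is low: validity is not in question, and neither the primary outcome nor its analysis is affected.

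**What to change.** In section 11.1.2:

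1. Include the closest enrollment item as a covariate in each risk-behavior comparison: the enrollment partner count (CSBQ or ICAP Section 4, stating which) for number of partners, and the enrollment condom-use item for condom use.
2. Name the methods: rank ANCOVA or a count model for partners, with CSBQ codes 777 and 999 set to missing, and an ordinal model for condom use. State which questionnaire item supplies the ordered condom-use categories and which supplies the count since the previous visit.
3. State that the enrollment windows (12 months in the CSBQ, 6 months in ICAP) differ from the follow-up window, so that enrollment values are covariates and no change scores are formed.
4. Reconcile section 10.4.14 and the section 10.5 list with sections 9.5 and 12.2 on whether the CSBQ is given at follow-up.
5. Optionally, say that the baseline table is descriptive and carries no significance tests.

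The cost is SAP wording, one covariate per model, and clarification of the assessment schedule and items. No additional visit is needed for the covariate. The one drawback is that section 11.1.1 rules out imputation, so participants without the enrollment item drop out of the adjusted analysis. Their number should be reported by arm.

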11.1.3 Sample Size

pilot RCT will be insufficiently powered to provide definitive efficacy data on retention and adherence for two study arms at 90 days. Yet, the pilot data is needed to determine recruitment and attrition rates, as well as means and standard deviations for key measures that will be needed to plan a definitive trial of ED-initiated

PrEP. For illustrative purposes we have included the following table of powers based on different retention in care rates in the control and experimental groups with the assumption that those retained in care will be using PrEP. This analysis assumes initial groups sizes of 40 and 40. The test statistic used is the two-sided Z test with pooled variance. The significance level of the test was targeted at 0.0500.

Power	Control Group	Experimental (iPrEP) Group	Difference in Proportions
	Retained in Care/PrEP	Retained in Care/PrEP	
0.0812	50%	55%	5%
0.1571	50%	60%	10%
0.2859	50%	65%	15%
0.4581	50%	70%	20%
0.6474	50%	75%	20%
0.8166	50%	80%	30%
0.9327	50%	85%	35%

The 50% follow-up rate for the control arm is based on and manuscript by Bogoch et als. entitled “Attrition Between the Emergency Department and Clinic Among Individuals Presenting for HIV Non-occupational Post exposure Prophylaxis published in *Clinical Infectious Diseases* in 2014.⁷⁴ The authors found that only 54% of patients seen in the ED for non-occupational post-exposure prophylaxis attended their first follow-up post-exposure clinic visit. This study did use appointment reminders but not the degree of facilitated linkage that will be used for the described ED PrEP program. In Project BRIEF, the HIV testing program described in the preliminary studies, the follow-up rate for newly infected HIV patients was 85%. Given that this will be the first effort at PrEP screening, initiation and linkage in the Emergency Department we do not expect to achieve the same degree of retention in care as we did for follow-up in Project BRIEF.

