12.1.2 Human Subjects Involvement, Characteristics, and Design

Aim 1 includes examining the impact of iPrEP initiation in the ED by providing a 14-day PrEP “starter pack” and creating linkage with the primary outcome being PrEP usage at 90-days post index visit compared to the linkage only arm, as well as a number of exploratory secondary outcomes including PrEP initiation

and use at 30 and 60 days. We also will collect data on recruitment and attrition rates, as well as means and standard deviations for key measures that will be needed to plan a definitive trial of ED-initiated PrEP.

For Aim 1, we will perform a randomized controlled clinical trial to compare the impact of immediate PrEP initiation (iPrEP) in the ED by providing a PrEP “starter pack” with facilitated linkage alone. The primary outcome is PrEP usage at 90-days post PrEP initiation visit. Participants will provide written informed consent for study participation. The consent to participate will also include 1) consent for investigators to collect prospectively collect clinical and sociodemographic data via medical record review and electronic data capture from the electronic health record. We anticipate 80 patients participating in the study associated with Aim 1.

Study procedures:

Aim 1: 80 PrEP eligible patients will be randomized 1:1 to either the experimental (iPrEP) arm or standard (outpatient PrEP) initiation arm. Patients in the iPrEP arm will receive a 14-day starter pack of PrEP and facilitated linkage. Patient in the control arm will receive facilitated linkage only. Patients in both arms will be followed for 90-days with telephone call follow-up visits scheduled for 30, 60 and 90 days post enrollment. Patients will be asked to complete satisfaction and medication adherence questionnaires at each scheduled follow-up

The setting of the human subjects' will be Mount Sinai Beth Israel Emergency Department.

Subject populations: The study population will include patients recruited in the Emergency Department at Mount Sinai Beth Israel Hospital

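### The power table in 11.1.3 is for a pooled Z test, but 11.1.2 plans Fisher exact intervals, which give 3 to 9 points less power on the conventional 95% reading; one difference cell is also misprinted

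*Combined protocol and SAP*

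**What the plan says.** Section 11.1.3 (Sample Size) says that the pilot "will be insufficiently powered to provide definitive efficacy data on retention and adherence", and introduces its table with: "For illustrative purposes we have included the following table of powers". The basis of the table is set out in full:

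- Group sizes: "This analysis assumes initial groups sizes of 40 and 40".
- Test: "The test statistic used is the two-sided Z test with pooled variance".
- Level: "The significance level of the test was targeted at 0.0500".
- Rates: control is 50% in every row; iPrEP runs from 55% to 85% in steps of 5 points.

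The printed powers are 0.0812, 0.1571, 0.2859, 0.4581, 0.6474, 0.8166 and 0.9327. The difference column reads 5%, 10%, 15%, 20%, 20%, 30%, 35%.

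Section 11.1.2 describes the analysis itself. The primary outcome "will be compared with proportions and Fisher's exact derived confidence intervals". It mentions no Z test, and it does not give the confidence level, the parameter or the version of the interval.

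**The concern.** A power table should describe the comparison that will be made. Here the table is for one procedure and the analysis section plans another. With 40 per arm the two are not interchangeable: a conventional Fisher exact interval is more conservative than the pooled Z test, so the printed powers would overstate what the planned comparison can show.

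The difference column also lists 20% twice, once beside a power of 0.4581 and once beside 0.6474. A reader who uses that column finds two powers for the same difference.

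The table is the plan's only quantitative statement of what 80 patients can show about the primary outcome, and the pilot is meant to inform a definitive trial. The table should therefore be right for the method in use, even though nothing in this pilot is decided by it.

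**Working it through.** **Inputs.** From 11.1.3: 40 per arm, control rate 0.50, iPrEP rates 0.55 to 0.85, two-sided level 0.05. The 1:1 allocation is in 12.1.2. One assumption is added: the intervals in 11.1.2 are conventional two-sided 95% intervals, so that they exclude no difference exactly when the two-sided Fisher p-value is at most 0.05.

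**Method.** Let *a* and *b* be the numbers of successes out of 40 in control and iPrEP. There are 41 × 41 = 1,681 possible results. For any rejection rule,

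power = Σ over (*a*, *b*) of Bin(*a*; 40, 0.50) × Bin(*b*; 40, p_iPrEP) × [1 if the rule rejects, 0 otherwise].

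The pooled Z rule rejects when |Z| ≥ 1.96, where Z = ((*b* − *a*)/40) / √(p̄(1 − p̄) × 2/40) and p̄ = (*a* + *b*)/80. The Fisher rule rejects when the two-sided Fisher p-value is at most 0.05.

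**Results.** The pooled Z column reproduces the plan's figures first; the mid-p column is twice the one-sided mid-p.

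| Control vs iPrEP | Printed | Pooled Z | Fisher | Printed − Fisher (points) | Mid-p |
|---|---|---|---|---|---|
| 50% vs 55% | 0.0812 | 0.0812 | 0.0506 | 3.1 | 0.0812 |
| 50% vs 60% | 0.1571 | 0.1571 | 0.1078 | 4.9 | 0.1571 |
| 50% vs 65% | 0.2859 | 0.2859 | 0.2130 | 7.3 | 0.2856 |
| 50% vs 70% | 0.4581 | 0.4581 | 0.3683 | 9.0 | 0.4569 |
| 50% vs 75% | 0.6474 | 0.6474 | 0.5585 | 8.9 | 0.6443 |
| 50% vs 80% | 0.8166 | 0.8166 | 0.7494 | 6.7 | 0.8109 |
| 50% vs 85% | 0.9327 | 0.9327 | 0.8975 | 3.5 | 0.9269 |

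The printed powers are therefore not miscalculated; they belong to the pooled Z test.

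**Where the two rules differ.** The pooled Z test rejects and Fisher does not in 72 of the 1,681 results; the reverse never happens. Defining the two-sided Fisher p-value as twice the one-sided value gives the same decision in all 1,681. When both rates are 50%, the exact type I error is 0.0567 for the pooled Z test, above the nominal 0.05, and 0.0330 for Fisher.

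**Example with 20/40 in control.**

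- iPrEP 29/40: p̄ = 49/80 = 0.6125, difference = 0.225, standard error = √(0.6125 × 0.3875 × 0.05) = 0.1089, Z = 2.07, p = 0.039. Fisher p = 0.066.
- iPrEP 30/40: pooled Z p = 0.021, Fisher p = 0.037.

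The smallest iPrEP count that excludes no difference is 29 under pooled Z and 30 under Fisher.

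**Difference cell.** 75% − 50% = 25%, not 20%. The power in that row, 0.6474, is the value for 50% vs 75%, so only the difference cell is wrong.

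**The case against.** The strongest reply is that only the 20% cell is an error without conditions. Section 11.1.3 states its test, level and group sizes openly, and its powers are correct for that test. Section 11.1.2 plans estimation and sets no rejection rule, so the 3 to 9 points depend on a reading that the plan does not spell out. Other readings give smaller gaps: at most 0.6 points for the doubled one-sided mid-p, about 2 to 8 points if half the observed table's probability is subtracted from the two-sided Fisher p-value, and 0.6 to 2.3 points for Boschloo's unconditional test. The table is also labelled illustrative, does not set the sample size, and is tied to no power target or go/no-go rule.

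Much of this stands, and it is why the point is minor and its size conditional. It does not remove the mismatch. The Z test is named in one section and absent from the other however the interval is read, and the plan mentions neither a mid-p nor an unconditional version. The missing parameter does not affect the power: under the conditional test, excluding no difference is the same decision for an odds ratio and for a risk difference.

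A further objection is that 40 analysed per arm ignores dropout. That is fair as a comment on the table, but 40 per arm is the table's own stated assumption and is used in both columns compared here.

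**Conclusion.** The concern holds, at minor severity. The power table is for a test that 11.1.2 does not plan. If the planned intervals are conventional 95% Fisher exact intervals and 40 per arm are analysed, the printed powers are 3.1 to 9.0 points too high. The gap is largest at 50% vs 70% (0.4581 against 0.368), and the 50% vs 80% row drops below 0.80. The 95% level and the conventional version are assumptions, because 11.1.2 states neither. The misprinted difference needs no assumption: 20% should read 25%. Neither point affects the sample size of 80.

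**What to change.** 1. In 11.1.2, state that the interval is the conventional two-sided 95% Fisher exact confidence interval, and name the parameter it is for.
2. In 11.1.3, replace the Z-test sentence with: 'Power is by exact enumeration with 40 per arm, as the probability that the 95% Fisher exact interval of 11.1.2 excludes no difference.'
3. Restate the power column as 0.051, 0.108, 0.213, 0.368, 0.559, 0.749, 0.898.
4. Correct the difference in the 50% vs 75% row from 20% to 25%.

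If the sponsor intends another interval version, 11.1.2 should name it and the column should be computed for that version. Naming the pooled Z test as the analysis would also remove the mismatch, but it would change the planned primary comparison.

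The cost is a few sentences, one recalculated column and one cell, with no change to sample size, visits or data collection. The displayed powers become 3 to 9 points less favourable.
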